6.2.3 Safety Analysis

To address Hypothesis 2.1 (*Adverse events will not differ by greater than 10% between treatments*), type and frequencies of adverse events will be presented descriptively by treatment. A magnitude of difference of less than 10% will be considered as similar between treatments.

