2 STUDY OBJECTIVES

2.1 Primary Objectives (or Aims)

Aim 1. To determine the optimal treatment duration of dynamic supported mobility (DSM) treatment in infants and toddlers with cerebral palsy, between 6 to 24 weeks of treatment.

Hypothesis 1.1. Gross motor ability (measured by the GMFM-66) will exceed individual predicted values in infants and toddlers with cerebral palsy after 12, 18, and 24 weeks of DSM treatment, and gains will be maintained at 3, 6 and 12 month follow-up points.

Hypothesis 1.2. Gross motor function gains will be positively related to the amount of motor error, variability and engagement experienced during DSM treatment.

Aim 2. To determine the futility of dynamic supported mobility compared to conventional rehabilitation in infants and toddlers with cerebral palsy.

Hypothesis 2.1. The frequency of adverse events among participants who receive DSM treatment and those who receive conventional (CONV) treatment will not differ by greater than 10 percent.

Hypothesis 2.2. Participants who receive DSM treatment will demonstrate significantly greater improvements in gross motor ability (measured by the GMFM-66) than participants who receive equal amounts of CONV treatment, and these differences will be maintained at each follow-up point.

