5.3 Safety Evaluation

Subject safety will be monitored by adverse events. Anticipated and unanticipated adverse events will be recorded to confirm that DSM treatment does not pose greater risks than current interventions.

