6.2 Statistical Methods

6.2.1 Baseline Data

Baseline characteristics for the total sample and by treatment group will be summarized by standard descriptive summaries (including mean, standard deviation, median, minimum, maximum and range for continuous variables and frequency counts and percentages categorical variables). We will also report the 95% confidence interval for pertinence means and proportions. Baseline characteristics in each group will be compared using two-sample tests, including t-tests, the Mann-Whitney test, and chi-square tests, as appropriate for the respective type of data.

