6.3 Sample Size and Power

This is a proof of concept futility study and to keep the number of participants to the minimum necessary, sample size estimation was not driven to achieve a specific effect size or statistical power, but rather to derive estimates and confidence intervals. A minimum of 15 subjects receiving a novel treatment has been recommended for early studies of dose-response and futility in neurorehabilitation.⁵¹ We also calculated predicted change and 95%

confidence intervals for both treatments. Predicted change after DSM treatment was determined from the data of the four pilot children who would meet the proposed selection criteria. A mean GMFM-66 increase of 5.3 was observed after six weeks of treatment. Assuming such change will be doubled after 12 or more weeks of treatment, a 10.6 increase from baseline is predicted as a minimum change after DSM treatment. Predicted change after CONV treatment was determined from maximum change in published GMFM-66 scores over six months in a 24 month old child classified as GMFCS level II.⁵⁵ A 1.8 increase from baseline is predicted after CONV treatment. We estimated that with a sample size of 17 participants receiving each treatment, a 2-sided 95% confidence interval for the difference in GMFM-66 will extend +/- 6 from the observed difference assuming that the common standard deviation (SD) is 9 (nQuery Advisor 6.0), which was larger than observed in the pilot data for a conservative estimate. An additional 8 children (4 in each group) will be enrolled to account for an anticipated attrition rate of 20%. Based on random assignment, 21 participants will receive DSM treatment, and another 21 will receive CONV treatment.

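### Section 6.2.3 calls the arms similar in safety whenever the observed adverse-event difference is under 10%, with no confidence interval; at 21 to 30 children per arm that label is weak evidence

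*Combined protocol and SAP*

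**What the plan says.** Hypothesis 2.1 sits under Aim 2 in section 2.1 (Primary Objectives). It states that adverse-event frequency among children on DSM and "those who receive conventional (CONV) treatment will not differ by greater than 10 percent". Section 5.3 gives the purpose of recording events: "to confirm that DSM treatment does not pose greater risks than current interventions".

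Section 6.2.3 is the whole analysis of this hypothesis. It restates it as "Adverse events will not differ by greater than 10% between treatments", says that "type and frequencies of adverse events will be presented descriptively by treatment", and then adds a verdict: "A magnitude of difference of less than 10% will be considered as similar between treatments".

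No section attaches an interval or a test to this comparison. The only general promise of an interval for proportions, "We will also report the 95% confidence interval for pertinence means and proportions", is in section 6.2.1 and concerns baseline data. Section 6.3, however, says that the sample size was chosen without a power target, "but rather to derive estimates and confidence intervals".

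On arm size, section 6.3 plans that "21 participants will receive DSM treatment, and another 21 will receive CONV treatment". Section 3.3.2 plans 60 enrolled and 42 evaluable, which is 30 enrolled per arm if the split is even.

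**The concern.** A descriptive safety table in a small exploratory trial is normal. The problem is the sentence that turns the point estimate into a conclusion. With this many children, an observed difference below 10 points is compatible with a true difference well above it, and the plan gives the reader nothing that shows this.

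The rule is also not fully defined. The plan does not say whether 10% means percentage points or a relative difference, or whether it counts children with an event or events. Hypothesis 2.1 admits a difference of exactly 10%, while section 6.2.3 requires less than 10%. At 30 per arm three children is exactly 10%, so the two wordings can give opposite answers.

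Few events are expected (section 8.4.1), and the five-child pilot had none (section 1.3). Low rates make the label easy to earn. A trial that follows the plan to the letter could report Hypothesis 2.1 as supported while a sizeable excess on DSM remains open, and the trial is meant to inform a decision about Phase III (section 3.1).

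**Working it through.** **The plan's only precision figure.** Section 6.3 gives ±6 for the GMFM-66 difference with 17 per arm and SD 9. The formula 1.96 × SD × √(2/n) gives 1.96 × 9 × √(2/17) = 6.05, so the figure is reproduced. Nothing comparable is given for adverse events.

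**Inputs.** Cut-off of 10 percentage points, strict inequality (6.2.3). n = 21 per arm (6.3) or 30 per arm (3.3.2, even split assumed). Endpoint assumed to be children with at least one adverse event. Conventional-arm rates of 2%, 5% and 10% are assumptions, because section 8.4.1 says only that incidence should be low.

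**What the rule means in children.** 2/21 = 9.5% and 3/21 = 14.3%; 2/30 = 6.7% and 3/30 = 10.0%. At either size, the label is given when the arms differ by at most two children.

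**Probability of the label.** With X₁ ~ Bin(n, p + δ) and X₂ ~ Bin(n, p), sum the exact joint probabilities over |x₁ − x₂|/n < 0.10:

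| Rate p | True excess δ | n = 21 | n = 30 |
|---|---|---|---|
| 2% | 0 | 0.989 | 0.974 |
| 5% | 0 | 0.927 | 0.869 |
| 10% | 0 | 0.809 | 0.725 |
| 2% | 10 points | 0.619 | 0.413 |
| 5% | 10 points | 0.588 | 0.414 |
| 10% | 10 points | 0.553 | 0.409 |
| 2% | 20 points | 0.199 | 0.065 |
| 5% | 20 points | 0.221 | 0.090 |
| 10% | 20 points | 0.245 | 0.118 |

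If exactly 10% also counts, as Hypothesis 2.1 allows, the n = 21 column is unchanged. At n = 30 the 10-point rows rise to 0.619, 0.594 and 0.567.

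**One labelled result.** Take 4/21 on DSM against 2/21, an observed difference of 9.5 points. The Wilson 95% limits are 0.077 to 0.400 for 4/21 (0.190) and 0.027 to 0.289 for 2/21 (0.095). The Newcombe limits for the difference are:

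- lower: 0.095 − √[(0.190 − 0.077)² + (0.289 − 0.095)²] = −0.130
- upper: 0.095 + √[(0.400 − 0.190)² + (0.095 − 0.027)²] = +0.316

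Twice as many children are affected, the interval runs from −13 to +32 points, and the label is *similar*.

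**No events at all.** 0/21 against 0/21 has Newcombe limits of ±15.5 points; 0/30 against 0/30 has ±11.4.

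**All possible results.** Over every pair of counts, no two-sided 95% Newcombe interval lies wholly within ±10 points at 21 or 30 per arm. The Agresti-Caffo interval, which is narrower when counts are low, admits only 0/30 against 0/30 (±8.5) and its mirror image 30/30 against 30/30. It admits nothing at 21, where 0/21 against 0/21 gives ±11.8.

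On the one-directional question of whether a 10-point DSM excess is excluded, the Newcombe upper limit falls below +10 in 2 of the 104 labelled tables at n = 21 and 6 of the 149 at n = 30. Those with low counts are 0/21 v 2/21 (upper +7.4), 0/30 v 1/30 (+8.3), 0/30 v 2/30 (+5.7) and 1/30 v 3/30 (+8.2). In each, DSM has fewer affected children.

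**How often a label leaves +10 open.** With truly equal arms at the three rates, the share of labelled results whose 95% upper limit is +10 or more is:

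| Method | n = 21 | n = 30 |
|---|---|---|
| Newcombe | 93–96% | 75–93% |
| Agresti-Caffo | 78–93% | 45–87% |

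**Expected precision.** The average Newcombe 95% half-width at equal rates of 5% and 10% is 18.2 and 20.5 points at n = 21, and 14.4 and 16.7 at n = 30.

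**The case against.** The strongest reply is that the 10-point row is measured at the cut-off itself. Any rule that cuts at 10 points will pass a large share of trials whose true difference is 10 points. At a true 20-point excess the label falls to 20–25% (n = 21) and about 6–12% (n = 30), so the rule does carry information about large differences. That is correct, and the weakness should be stated as lying around the plan's own margin. It does not rescue the rule, because that margin is where Hypothesis 2.1 makes its claim.

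Second, 90% limits are often used for equivalence or non-inferiority. With 90% Newcombe limits, 0/30 against 0/30 falls inside ±10, and the share of labelled results that leave +10 open (equal arms) drops to 76–83% at n = 21 and 41–71% at n = 30. The conclusion weakens but does not reverse, and the plan's own convention is two-sided 95% (sections 6.2.2 and 6.3).

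Third, if events rather than children are counted, none of the binomial figures apply. With 72 sessions planned per child and minor bumps expected, that reading is plausible. This stands as a limit on the numbers, and it is a further reason to define the endpoint.

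Fourth, the study is exploratory, states minimal risk and ties no decision to the label. Section 8.4.1 has its own trigger of adverse events in more than 15% of all participants. No sentence says outright that greater risk will be declared excluded; that reading joins section 5.3 to section 6.2.3. This limits the consequence. The 15% trigger pools the arms, however, so it does not answer the between-arm question.

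**Conclusion.** The concern holds. The only planned analysis of a primary-aim hypothesis is a label based on a point estimate, and at this sample size the label discriminates poorly around its own margin: 55–62% of trials at 21 per arm, and 41% at 30, would be called similar with a true 10-point DSM excess. No possible result at either size puts the whole two-sided 95% Newcombe interval within ±10 points.

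The figures rest on three assumptions: percentage points, children with at least one event, and conventional-arm rates of 2–10%. The missing interval and the undefined 10% do not depend on them. The fault is the unqualified verdict; low power is not the complaint, since section 6.3 openly disclaims a power target. The harm is to interpretation, because no safety action follows from the label. The change is worth making because it is cheap.

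**What to change.** - **Section 6.2.3:** keep the planned tables of type and frequency. Replace the verdict sentence with the number of children with at least one adverse event in each arm and the absolute risk difference (DSM minus CONV), with a Newcombe or exact 95% confidence interval.
- **The 10%:** if it stays as a reference value, define it as percentage points of children with at least one adverse event, and word the boundary the same way in sections 2.1 and 6.2.3.
- **Hypothesis 2.1 and section 5.3:** reword the hypothesis as estimating the difference, and change the stated purpose in 5.3 from confirming to describing.
- **Expected precision:** state that the 95% interval is expected to be wider than ±10 points (average half-width about 18 and 14 points at 21 and 30 per arm for a 5% rate, 21 and 17 for 10%), and that an observed difference under 10 points will not be read as demonstrated similar safety.

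The cost is one interval in the safety table and wording changes in three sections, one of which holds a primary-aim hypothesis. No data are added. The trial gives up a claim of demonstrated similar safety, which it is not large enough to support.

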6.3 Sample Size and Power

This is a proof of concept futility study and to keep the number of participants to the minimum necessary, sample size estimation was not driven to achieve a specific effect size or statistical power, but rather to derive estimates and confidence intervals. A minimum of 15 subjects receiving a novel treatment has been recommended for early studies of dose-response and futility in neurorehabilitation.⁵¹ We also calculated predicted change and 95%

confidence intervals for both treatments. Predicted change after DSM treatment was determined from the data of the four pilot children who would meet the proposed selection criteria. A mean GMFM-66 increase of 5.3 was observed after six weeks of treatment. Assuming such change will be doubled after 12 or more weeks of treatment, a 10.6 increase from baseline is predicted as a minimum change after DSM treatment. Predicted change after CONV treatment was determined from maximum change in published GMFM-66 scores over six months in a 24 month old child classified as GMFCS level II.⁵⁵ A 1.8 increase from baseline is predicted after CONV treatment. We estimated that with a sample size of 17 participants receiving each treatment, a 2-sided 95% confidence interval for the difference in GMFM-66 will extend +/- 6 from the observed difference assuming that the common standard deviation (SD) is 9 (nQuery Advisor 6.0), which was larger than observed in the pilot data for a conservative estimate. An additional 8 children (4 in each group) will be enrolled to account for an anticipated attrition rate of 20%. Based on random assignment, 21 participants will receive DSM treatment, and another 21 will receive CONV treatment.

7 SAFETY MANAGEMENT

7.1 Clinical Adverse Events

Clinical adverse events (AEs) will be monitored throughout the study.

7.2 Adverse Event Reporting

Since the study procedures are not greater than minimal risk, SAEs are not expected. If any unanticipated problems related to the research involving risks to subjects or others happen during the course of this study (including SAEs) they will be reported to the IRB in accordance with CHOP IRB SOP 408: Unanticipated Problems Involving Risks to Subjects. AEs that are not serious but that are notable and could involve risks to subjects will be summarized in narrative or other format and submitted to the IRB at the time of continuing review.

8 STUDY ADMINISTRATION

8.1 Treatment Assignment Methods

8.1.1 Randomization

After the initial GMFM-66 score from Assessment 1 is obtained, participants will be randomized to either the CONV or DSM treatment, using a randomization scheme to stratify by baseline motor ability. This will ensure that the groups do not differ in motor ability at baseline. Participants will also be randomly assigned to either the primary or secondary research therapist who will each provide both types of treatments, to minimize any differences related to individual therapist. A blinded assessor will collect all outcomes measures. Blinding of participants to treatment group is not feasible with the proposed interventions.

8.1.2 Blinding

A blinded assessor will collect all outcomes measures. Blinding of participants to treatment group is not feasible with the proposed interventions.

8.2 Data Collection and Management

Hard copies of case report forms and source data will be stored in a locked cabinet in a locked office. Electronic source data will be stored on a network share drive with access controlled by the PI. All data will be entered and stored in a project-specific REDCap (Research Electronic Data Capture) database. The database will be password-protected and daily backups will be stored. It will incorporate range checks and between-variables consistency checks to ensure quality control.

The electronic postural control data will be shared with researchers ([name] and his team) at University of Nebraska Omaha, who are experts in nonlinear analysis of biomechanical data and will assist our team in interpreting these data. A portion of the treatment videos will be shared with motor development experts ([name] and her team) at New York University (NYU) who will assist our team in coding the videos for structure of walking behavior using their established methods of detailed infant movement analysis. The data files will be stored in a secure, password protected electronic location, and will be regularly backed up.

8.3 Confidentiality

All data and records generated during this study will be kept confidential in accordance with Institutional policies and HIPAA on subject privacy and that the Investigator and other site personnel will not use such data and records for any purpose other than conducting the study. Participants will be assigned a unique identifier that contains no protected health information. Access to all data will be controlled by the PI. No identifiable data will be used for future study without first obtaining IRB approval. The investigator will obtain a data use agreement between the provider (the PI) of the data and any recipient researchers (including others at CHOP) before sharing either limited or identifiable datasets.

8.4 Regulatory and Ethical Considerations

8.4.1 Data and Safety Monitoring Plan

The incidence of adverse events is expected to be low in this single-site minimal risk research. The PI will be responsible for monitoring the data and safety of all participants. All study procedures will receive IRB approval prior to recruitment or enrollment of participants. In addition to the data management procedures outlined above, the PI will hold biweekly study team meetings to evaluate the safety and progress of all research procedures. Standard procedures for all data collection methods will be reviewed at the start and periodically throughout the study. Data checks for errors will be performed prior to analysis. Training log review and random video checks will be conducted regularly to ensure that the rehabilitation programs are delivered as intended. The PI will be actively involved in reviewing the progress of each study participant and will bring to the attention of the IRB adverse events and unexpected problems. Unexpected safety concerns will also be communicated with the NINDS Program Official in accordance with study regulations.

Additionally, if we experience adverse events in more than 15% of total participants, we will appoint a Study Monitoring Committee to review the safety events that occurred and monitor safety for the remaining duration of the study.

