3.3.2 Total Number of Study Sites/Total Number of Subjects Projected

All testing procedures and interventions will occur in the Center for Rehabilitation at CHOP. Sixty participants with CP between the ages of 1-3 years will be recruited for the study. It is expected that enrollment of 60 participants will produce 42 evaluable datasets.

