8.5 Recruitment Strategy

Our goal is to enroll 16 and 20 participants in Years 1 and 2, respectively. The primary avenue for recruitment will be through the Neonatal Follow-up clinic at CHOP, directed by [name]. Eligible patients seen in CHOP's CP clinic and those with CP who are receiving services at the Center for Rehabilitation will also be invited to participate. Potential candidates who are not CHOP patients will be reached through the internet (www.clinicaltrials.gov) and the CHOP Research Institute website (http://www.research.chop.edu/research/clinical_research/) and mailings to local clinicians, including therapists, developmental pediatricians, and pediatric neurologists. All recruitment materials will receive prior ethics approval.

We will also be working with the Recruitment Enhancement Core, including posting messages in the "This Week at CHOP" email to employees. Additionally, we will also work with the National Rehabilitation Information Center (NARIC) to send out notifications regarding our study. For both the "This Week at CHOP" and NARIC postings, we will use the approved blurb below in Section 7.01 (5.0) that is currently used on CHOP's public website.

We will also work with PeRC to distribute mailings to potential participants. PeRC will provide the study team with a list of names and contact information for mailings. Potential participants will be asked to call or email a member of the study team for additional information. Interested participants will be contacted via phone or email for information about the study.

We will also work with Research Communications to create a short video about our study. This video will be distributed to rehabilitation therapists and early intervention agencies at CHOP and in the community outside of CHOP. This video can be shared with colleagues and/or caregivers of potential participants.

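### The 15% adverse-event trigger for a Study Monitoring Committee pools both arms, so it responds weakly to an excess in DSM alone; a by-arm count on planned arm sizes would close the gap

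*Combined protocol and SAP*

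**What the plan says.** Section 8.4.1 (Data and Safety Monitoring Plan) makes the PI responsible for safety, with study team meetings every two weeks. Adverse events and unexpected problems go to the IRB, and unexpected safety concerns also go to the NINDS Program Official. It then adds one escalation rule: "if we experience adverse events in more than 15% of total participants, we will appoint a Study Monitoring Committee". The rule has no by-arm rate and no between-arm difference. It does not say whether the total is the planned number or the number enrolled so far.

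Elsewhere the safety question is comparative. Section 5.3 records events to "confirm that DSM treatment does not pose greater risks than current interventions". For Hypothesis 2.1, section 6.2.3 says: "A magnitude of difference of less than 10% will be considered as similar between treatments". That criterion is descriptive and is not linked to the committee.

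The planned total differs between sections. Section 6.3 says that "21 participants will receive DSM treatment, and another 21 will receive CONV treatment". Section 3.3.2 says: "It is expected that enrollment of 60 participants will produce 42 evaluable datasets". Section 8.5 says: "Our goal is to enroll 16 and 20 participants in Years 1 and 2, respectively".

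**The concern.** A pooled percentage halves the weight of an excess that sits in one of two equal arms. An excess confined to DSM is not far-fetched. Section 8.4.2 says that DSM encourages falls, although over mats and in a harness that limits impact, and the harness itself calls for skin checks. The sponsor has decided that above some event rate a committee should look at the data. If that rate responds poorly to an excess in the experimental arm, the committee may not exist in the situation where it would be most useful.

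The undefined denominator is a second, smaller problem. Two people applying the rule in good faith could appoint the committee at different counts.

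**Working it through.** **Inputs.** The 15% threshold is strict (more than) and comes from section 8.4.1. Arms of 21 and 21 come from section 6.3. The total of 60 comes from section 3.3.2; 30 per arm is an assumption. I count children with at least one event. The event risks below are assumptions, because the documents give none.

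**The plan's own sample size.** Section 6.3 states that "with a sample size of 17 participants receiving each treatment, a 2-sided 95% confidence interval for the difference in GMFM-66 will extend +/- 6", "assuming that the common standard deviation (SD) is 9". Check: 1.96 × 9 × √(2/17) = 6.05, which agrees. Adding 8 gives 34 + 8 = 42, and 8/42 = 19%, close to the stated 20% attrition. Going from 60 to 42 would instead be a loss of 18/60 = 30%. So both 42 and 60 are carried forward. The 15% threshold has no derivation in the documents.

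**Counts at which each rule fires, on planned totals.**

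- Pooled, N = 42: 0.15 × 42 = 6.3, so 7 children are needed.
- Pooled, N = 60: 0.15 × 60 = 9.0, and exactly 15% does not fire, so 10 are needed.
- By arm, 21: 0.15 × 21 = 3.15, so 4 are needed.
- By arm, 30: 0.15 × 30 = 4.5, so 5 are needed.

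**Worst case (no CONV events).**

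- N = 42: 6/42 = 14.3% does not fire, while DSM stands at 6/21 = 28.6% (two-sided Fisher p = 0.021 against 0/21).
- N = 60: 9/60 = 15.0% does not fire, while DSM stands at 9/30 = 30.0% (p = 0.002 against 0/30).
- N = 36, the two-year goal in section 8.5: 5/36 = 13.9% does not fire, while DSM stands at 5/18 = 27.8%.

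**Chance of firing at full enrolment.** Let D and C be independent binomial counts in arms of size m. The pooled rule fires with probability P(D + C ≥ 7) or P(D + C ≥ 10). The by-arm rule fires with probability 1 − P(D ≤ 3)·P(C ≤ 3), or 1 − P(D ≤ 4)·P(C ≤ 4). For example, at 25% and 5% with m = 21: 1 − 0.192 × 0.981 = 0.81.

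| Assumed risk, DSM / CONV | N = 42: pooled → by arm | N = 60: pooled → by arm |
|---|---|---|
| 25% / 5% | 45% → 81% | 41% → 90% |
| 20% / 10% | 45% → 69% | 41% → 79% |
| 5% / 5% | 0.4% → 3.7% | 0.1% → 3.1% |
| 10% / 10% | 12% → 28% | 7% → 32% |

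The by-arm figures also hold for both rules together: 7 children among 42 means at least 4 in one arm, and 10 among 60 means at least 5 in one arm.

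**Running denominator.** If the percentage is taken over children enrolled so far, the rule behaves differently. One event among six children in an arm is 16.7% and fires a by-arm rule; one among seven is 14.3% and does not. A simulation that checks after each child, and treats event status as known at entry (a simplification), gives two results:

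- A by-arm running rule fires in about 52% of trials when both risks are 5%.
- The existing pooled rule, read as a running rate, fires in about 85% (N = 42) or 87% (N = 60) of trials at 25% and 5%.

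**The case against.** The strongest case against the point has four parts.

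- **Safety is not unwatched before the trigger.** The committee rule is introduced as an addition to PI review, the two-weekly meetings and reporting to the IRB and NINDS. Section 7.2 adds IRB reporting of unanticipated problems and of notable non-serious events. Therapists know the treatment given, so staff could see an imbalance. This stands. A reader might infer that a DSM excess of nearly 30% would go without outside review; the documents do not support that, because the IRB is outside the study team. Only committee review is missing.
- **A zero rate in CONV is the extreme split.** Section 8.4.2 describes bumps and bruises as risks of any paediatric therapy session, so some CONV events are likely. With DSM at 25%, the pooled rule at N = 42 fires in 62% of trials if CONV is at 10%, and in 76% if CONV is at 15%. This stands: 28.6% and 30% are upper limits, not expected values.
- **The rule may be meant as a running rate.** It would then fire far more often, as shown above. This also stands, and it is why the result is conditional on the planned-total reading. It does not rescue the text, which leaves the reading open.
- **The 10-point criterion is not the committee's remit.** A reader might infer that the trigger fails a duty to police Hypothesis 2.1. Section 8.4.1 gives it no such purpose, and section 6.2.3 is a descriptive analysis. The two rules do not contradict each other.

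It can also be said that the study is classed as minimal risk and that the pilot had no adverse events. The pilot treated five children for six weeks; this trial treats for 24 weeks. A low expected event rate also keeps the by-arm rule cheap.

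**Conclusion.** The point holds in a limited form. The only rule for appointing a committee is pooled, has no by-arm condition and leaves its denominator open, while the plan's safety question compares the arms. On the planned-total reading and with no CONV events, up to 28.6% (N = 42) or 30% (N = 60, 1:1 assumed) of DSM children could have an event without a committee. At assumed risks of 25% and 5%, the rule fires in fewer than half of trials on either total.

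These sizes rest on the planned-total reading, on the assumed risks and on full enrolment. Nothing here contradicts another section or touches the efficacy analysis. The severity is therefore modest: a change worth considering because it is cheap.

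**What to change.** In section 8.4.1, keep the pooled rule, state that its denominator is the planned total, and add: *or in more than 15% of the planned number of participants in either treatment group*. That is 4 of 21 or 5 of 30, once sections 3.3.2, 6.3 and 8.5 are reconciled on the planned total. Writing the counts into the text would remove any doubt.

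Avoid an enrolled-to-date denominator unless a minimum arm size is set; without one, a single early event can fire the rule. With fixed counts, how often the data are checked does not change the overall chance of firing.

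The cost is one clause that uses the plan's own threshold and the committee it already provides for. The downside is that a committee would be appointed by chance more often, to the extent shown in the equal-risk rows of the table: small if both risks are 5%, but about 3 trials in 10 if both are 10%. In that event the committee reviews the events and monitors safety; the rule does not stop the trial.
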